5.10.3 Analysis of Laboratory Safety Parameter

Laboratory safety variables (continuous values) will be summarised by descriptive statistics and by visit.

- Clinical chemistry, haematology: absolute and change from screening to follow-up

The reference range indicator (normal, low, high) per variable will be summarised by frequencies.

- Urinalysis: absolute and shifts from screening to follow-up

Statistical Analysis Plan				
Trial ID	EudraCT-No.	Date	Status / Version-No.	Page
I8B-MC-ITST	2019-003493-13	15 Jul 2020	Final 1.0	36 of 47

Summaries will be performed by visit. All laboratory values will be listed by visit and subject number including flagging of values outside normal range (“NCS”: not clinically significant; “CS”: clinically significant). A listing of abnormal values will be presented in an end of text (EOT) listing. In case of a re-screening of a subject, it will be discussed at the DBR meeting which values should be included in the summary table (i.e. values from the first screening or values from the re-screening). The decision and the reason will be stated in the DBR meeting minutes. A footnote will be added to the summary table.

5.10.4 Analysis of Electrocardiograms

ECG data will only be collected and listed. No analysis is planned.

5.10.5 Analysis of Vital Signs

Vital signs data (absolute and change from Day -1 to follow-up) will be presented by individual listings. In addition, summaries will be presented using descriptive statistics. Qualitative vital signs data will be summarised in a frequency table. Summaries will be separated by visit or treatment period; on treatment periods summaries will be done by treatment and day. In addition to the pre-specified assessments in protocol Section 2, BP and pulse may be assessed at any time during the trial at the discretion of the Investigator. All these values will be listed. A listing of abnormal values including flagging of values outside normal range (“NCS”: not clinically significant; “CS”: clinically significant) will also be presented.

5.10.6 Analysis of Physical Examinations

Abnormal physical examinations will be presented.

5.11 Analysis of Other Exploratory Parameters

All other exploratory parameters will be presented for all subjects in the FAS by individual listings, summary tables and figures. All figures will be presented on linear scale. Individual profiles will be presented including all available data. Mean profiles will be presented including all data used in the statistical analysis.

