4.2 Endpoints

4.2.1 Primary endpoints:

- Time to recovery from hyperglycemia (time of correction bolus to time when PG = 140 mg/dL)

4.2.2 Secondary endpoints:

PD endpoints:

- $AUC_{(B-tPG140)}$, area under the PG curve but above 140 mg/dL from time of correction bolus (B) to time when PG is 140 mg/dL)
- $AUC_{(B-tPG180)}$, area under the PG curve but above 180 mg/dL from time of correction bolus (B) to time when PG is 180 mg/dL)
- Rate of change in PG (the change in PG at the time of bolus IMP administration to PG = 140 mg/dL measurement divided by the duration of time for this interval)
- PG_{max} , maximum observed plasma glucose

Clinical Trial Protocol				
Trial ID	EudraCT-No.	Date	Status / Version-No.	Page
I8B-MC-ITST	2019-003493-13	17 Jan 2020	Final 2.0	26 of 74

PK endpoint:

- t_{max} , time to maximum observed insulin concentration.
- Early 50% t_{max} , time to half-maximum before C_{max} .
- $AUC_{(0-15min)}$, are under the insulin curve from 0 to 15 minutes.
- $AUC_{(0-30min)}$, are under the insulin curve from 0 to 30 minutes.

4.2.3 Exploratory endpoints:

- Time to hyperglycaemia (PG > 240 mg/dL) after basal insulin suspension
- Peak ketone concentration after basal insulin suspension

4.2.4 Safety endpoints:

- Adverse Events

Further endpoints are defined in Section 13 and may be defined in the Statistical analysis plan (SAP).

Clinical Trial Protocol				
Trial ID	EudraCT-No.	Date	Status / Version-No.	Page
I8B-MC-ITST	2019-003493-13	17 Jan 2020	Final 2.0	27 of 74

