13.4.2 Analysis of the Secondary GD Endpoints

Subjects who did not keep identical insulin lispro doses for LY90014 and Humalog® for each day and period or had differences in the test meal will be excluded from the statistical analysis of the PK parameters.

Log-transformed PG AUCs and PG_{max} will be evaluated to estimate geometric means, ratios of geometric means of insulin lispro within LY900014 to Humalog, and their corresponding 95% CIs of the ratios using the mixed-effects model that includes treatment (LY900014, Humalog), period and sequence as fixed effects and subject as a random effect. The analysis will be performed separated by day (Day 1: meal test procedure with missed meal bolus , Day 2: pump suspension). In case of determination of baseline corrected AUCs to address possible inter-occasion variability, iAUCs will be analysed using the same model. Analysis of iAUCs will be based on untransformed endpoints, if negative values occurred. In this case, LSmeans, treatment differences in LSmeans, and corresponding 95% CIs for the treatment differences will be estimated from the model. The p-value on the difference between LSmeans will be used to determine statistical significance. The treatment ratios and 95% CIs for the ratios will be calculated using Fieller's theorem.

The same model without log transformation will be used for the analysis of the rate of change in PG and exploratory GD time parameters. Least-squares means, treatment differences in LSmeans, and the corresponding 95% CIs for the treatment differences will be estimated from the model. The p-value on the difference between least squares (LS) means will be used to determine statistical significance. The treatment ratios and 95% CIs for the ratios will be calculated using Fieller's theorem (Chow SC, Liu JP. 2009).

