4.4 Exploratory Endpoints

Evaluation of the exploratory endpoint time to hyperglycemia after basal insulin suspension will be performed on Day 2. The time will be calculated using the time of the basal insulin suspension until the time of the exact point of intersection with the target margin of 240 mg/dL.

The ketone concentration will be measured on Day 2. The peak of ketone concentration will be defined as the maximum of the measured ketone concentrations.

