5 STATISTICAL METHODOLOGY

5.1 Analysis Sets

The following analysis sets are defined in accordance with the International Council for Harmonisation (ICH)-E9 guidance (1):

Full Analysis Set (FAS)

The full analysis set (FAS) is based on the intention-to-treat principle and includes all subjects who were randomised. Subjects will contribute to the evaluation ‘as randomised’. PK and PD listings (subjects, who are in the FAS, but not in the mFAS will be identified) and the subject disposition and demographic and baseline characteristics will be based on the FAS.

Modified FAS (mFAS)

The modified FAS includes all subjects of the FAS who complete the study according to the sequence/treatment to which they are randomised. Subjects will contribute to the evaluation ‘as randomised’. Primary and secondary statistical analyses of PK and GD parameters will be conducted on the set of subjects who complete all treatment periods with the same dose and meal intake as the PK parameters and GD response are dependent on the insulin dose which is individualized by subject.

Safety Analysis Set (SFAS)

The safety analysis set includes all enrolled subjects that have received IMP at least once (basal rate) - whether or not they fulfilled all protocol requirements. Subjects in the safety set will contribute to the evaluation ‘as treated’. The safety analysis will be based on the safety analysis set.

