5.4 Missing, Unused and Spurious Data

All available data will be included in data listings and tabulations. Unless otherwise specified in Section 4, no imputation of values for missing data will be performed. Imputed values will be presented in data listings and will be flagged.

Missing statistics will be presented as "NC" (not calculable). For example, if individual values are 0, the geometric mean cannot be calculated and will be presented as "NC".

Variable specific information for imputing missing data is given in Section 4.

Statistical Analysis Plan				
Trial ID	EudraCT-No.	Date	Status / Version-No.	Page
I8B-MC-ITST	2019-003493-13	15 Jul 2020	Final 1.0	29 of 47

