5.5 Presentation of Results

5.5.1 Presentation of Summary Statistics and Individual Data

In general, continuous endpoints are summarized by the arithmetic mean, geometric mean, median, standard deviation, coefficient of variation (CV), geometric coefficient of variation, and minimum and maximum. Categorical variables will be presented using descriptive summary statistics including number of subjects and percentages. Percentages of subjects will be based on non-missing values.

All PK and PD endpoints will be summarised by treatment (LY900014 and Humalog) and dosing day (Day 1 and 2) using descriptive statistics and will be provided by Lilly using their SOP. All summary PD and PK parameters and mean plots will be presented for all subjects in the mFAS, which is reflective of the subjects used in the statistical analysis.

Individual PK and PD profiles will be plotted by treatment and dosing day. Individual profiles will be presented for all available data (FAS). Similarly, individual listing of PK and GD parameters will be presented for all subjects. The presentation of individual profiles and listings will be provided in the appendix of the CSR.

The safety endpoint and all tolerability assessments will be summarised using frequency tables or descriptive statistics and will be provided by Profil. For numeric data, individual as well as minimum and maximum values will be presented with the same number of decimal places as the raw data. Descriptive statistics, such as arithmetic mean and median values will be presented with an additional decimal place and standard deviation data with two additional decimal places as the raw data.

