5.8 Analysis of Secondary PD Endpoints

Subjects who did not keep identical insulin lispro doses for LY900014 and Humalog[®] for each day and period or had differences in the test meal will be excluded from the statistical analysis of the PD parameters.

Log-transformed PG AUCs and PG_{max} will be evaluated to estimate geometric LSmeans, ratios of geometric means of insulin lispro within LY900014 to Humalog[®], and their corresponding 95% CIs of the ratios using the mixed-effects model that includes treatment (LY900014, Humalog[®]), period and sequence as fixed effects and subject within sequence as a random effect.

Within the model the LS mean for each treatment as well as the difference of the LSmeans between the treatment groups and corresponding 95% CI will be calculated and exponentially back-transformed in order to find the estimated ratio between the insulin formulations and corresponding 95% CI.

The analysis will be performed separated by day (Day 1: meal test procedure with missed meal bolus, Day 2: pump suspension). In case of determination of baseline corrected AUCs (iAUC) to address possible inter-occasion variability, iAUCs will be analysed using the same model. Analysis of iAUCs will be based on untransformed endpoints, if negative values occurred. In this case, LS-means, treatment differences in LS-means, and corresponding 95% CIs for the treatment differences will be estimated from the model. The p-value on the difference between LS-means will be used to determine statistical significance. The treatment ratios and 95% CIs for the ratios will be calculated using Fieller's theorem.

The same model without log transformation will be used for the analysis of the rate of change in PG and exploratory PD time parameters. LS-means, treatment differences in LS-means, and the corresponding 95% CIs for the treatment differences will be estimated from the model. The p-

Statistical Analysis Plan				
Trial ID	EudraCT-No.	Date	Status / Version-No.	Page
I8B-MC-ITST	2019-003493-13	15 Jul 2020	Final 1.0	32 of 47

value on the difference between LS-means will be used to determine statistical significance. The treatment ratios and 95% CIs for the ratios will be calculated using Fieller's theorem [4].

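### Peak ketone on Day 2 is planned descriptively only; adding it to the existing crossover model would be a cheap exploratory improvement, not the repair of an error

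*SAP*

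**What the plan says.** Protocol 4.2.3 lists two exploratory endpoints, both after basal insulin suspension: time to PG above 240 mg/dL, and "Peak ketone concentration after basal insulin suspension". SAP 4.4 defines the second: "The peak of ketone concentration will be defined as the maximum of the measured ketone concentrations".

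SAP 5.8 extends the crossover model beyond the secondary endpoints: "The same model without log transformation will be used for the analysis of the rate of change in PG and exploratory PD time parameters". Protocol 13.4.2 has the same rule for exploratory GD time parameters. The output is LS-means, their difference with 95% CI, a p-value and a Fieller ratio. The log-scale part of SAP 5.8 covers only the PG AUCs and maximum PG.

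Protocol 13.4.6 leaves all other measurements to the SAP. SAP 5.11 then states: "All other exploratory parameters will be presented for all subjects in the FAS by individual listings, summary tables and figures". It adds individual profiles with all available data, and mean profiles restricted to data used in the statistical analysis.

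SAP 5.5.1 says "All PK and PD endpoints will be summarised by treatment (LY900014 and Humalog) and dosing day (Day 1 and 2) using descriptive statistics" and places the PD and PK summaries on the mFAS. Its list of statistics contains no treatment contrast and no confidence interval.

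**The concern.** Two endpoints of equal standing, measured in the same subjects on the same day, get different treatment. One has a within-subject estimate with a CI and the other has summaries by treatment. Protocol 5.7 justifies the crossover because each subject is their own control, and summaries by treatment do not use that pairing.

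The data are already scheduled. Protocol Table 3 calls for ketones every 30 minutes before the bolus, then at B and every 30 minutes to B + 5 h.

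What is at stake is small: how precisely the report can describe the difference in peak ketone between the two insulins. A comparison added later would be allowed, but protocol 13.2 classes analyses not specified in the SAP as post hoc.

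**Working it through.** **1. Where each exploratory endpoint lands.**

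| Endpoint | Type | SAP section | Planned output |
|---|---|---|---|
| Time to PG > 240 mg/dL | time | 5.8, through the class of exploratory PD time parameters | LS-mean difference, 95% CI, p-value, Fieller ratio and CI |
| Peak ketone | concentration | 5.11 | listings, summary tables, figures |

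SAP 5.7, 5.8 and 5.9 do not name ketones. SAP 5.5.2 says how model results are shown but assigns no model to ketones. The reference in SAP 5.11 to data used in the statistical analysis specifies no ketone analysis.

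**2. Samples available.** From B to B + 5 h: B, +30, +60, +90, +120, +150, +180, +210, +240, +270 and +300 min, which is 11 per period, plus those taken before the bolus.

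**3. What the summaries can and cannot give.** If geometric means are shown by treatment, a crude ratio can be read off. With log-scale SDs s1 and s2, the variance of the paired log ratio is (s1² + s2² − 2ρ·s1·s2)/n. The within-subject correlation ρ is not among the SAP 5.5.1 statistics, so the paired CI cannot be built from the summary tables. It can be built from the individual listings.

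**4. Illustrative width of the paired CI.** The plan has no ketone figure to reproduce. Its only variability figures are for the primary endpoint, in minutes, and do not carry over. CV and ρ below are therefore assumed; n = 24 is the planned number of completers.

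s = √ln(1 + CV²), giving 0.385, 0.555 and 0.703 for CV 40%, 60% and 80%.

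CI factor = exp[t(0.975, n − 2) × s × √(2(1 − ρ)/n)]

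Example, CV 60% and ρ = 0.5: exp[2.074 × 0.5545 × √(1/24)] = exp(0.2347) = 1.265.

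| CV, n = 24 | ρ = 0 | ρ = 0.3 | ρ = 0.5 | ρ = 0.7 |
|---|---|---|---|---|
| 40% | 1.259 | 1.213 | 1.177 | 1.135 |
| 60% | 1.394 | 1.320 | 1.265 | 1.199 |
| 80% | 1.524 | 1.422 | 1.347 | 1.259 |

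The 95% CI is the estimated ratio multiplied and divided by the factor.

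**5. Sensitivity run.** If omitting subjects with an additional or rescue bolus left 20 or 16 pairs (assumed), CV 60% at ρ = 0.3, 0.5 and 0.7 gives 1.361, 1.298 and 1.224 (n = 20), or 1.422, 1.346 and 1.259 (n = 16).

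**6. One-period subjects, on the FAS reading only.** Suppose k = 4 of 28 FAS subjects had ketone data on one treatment only, the same one for all four, and their log mean differed by d SD. The crude ratio then shifts by exp[k/(24 + k) × d × s]. With CV 60%, this is exp(0.143 × 0.5 × 0.5545) = 1.040 for d = 0.5, and 1.082 for d = 1. All these inputs are assumed.

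**The case against.** The strongest case is that the split is deliberate. The only exploratory objective (protocol 4.1.3) concerns blood glucose response. The glucose endpoint is modelled and the ketone endpoint is described. Protocol 13.2 also allows further exploratory analyses as deemed appropriate. This stands as far as it goes: nothing in the plan is wrong, and description is acceptable. But that objective is itself worded as a comparison of the two insulins, and a ratio with a CI serves a comparison better than two sets of summaries.

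A reader might infer that the plan makes a paired comparison impossible. It does not. SAP 5.11 lists individual values for all FAS subjects, so the paired ratio and its CI could be computed from the listings. What is missing is a planned estimate.

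A reader might also infer that one-period subjects will distort the ketone summaries. SAP 5.1 supports that only in part: "The full analysis set (FAS) is based on the intention-to-treat principle and includes all subjects who were randomised". If ketone counts as a PD endpoint, SAP 5.5.1 puts its summaries on the mFAS, which holds completers, and the 1.040 or 1.082 shift does not arise. The documents do not settle which section governs.

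Two practical objections also stand and shape the fix. A ketone analysis in SAP 5.8 should respect that section's equal-dose rule, since protocol 5.4 lets bolus doses change during the study. And omitting subjects given an additional bolus selects on a post-dose event (PG above 180 mg/dL at B + 2 h in protocol Table 3), while a peak before that time is unaffected by that bolus. Omission therefore belongs in a sensitivity run.

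**Conclusion.** The point holds as a cheap improvement to one exploratory result. Peak ketone has no planned within-subject ratio or 95% CI, although the paired data are scheduled and the model is already in use for the other exploratory endpoint. No primary or secondary conclusion is affected.

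The size of the gain cannot be stated, because the documents give neither a CV nor a within-subject correlation for ketones. The factors of 1.135 to 1.524 at n = 24 show only what a CI might look like for assumed CVs of 40% to 80% and correlations of 0 to 0.7. They do not measure a loss. Calling the present plan an error, or the planned summaries biased, would go beyond the documents.

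**What to change.** Add to SAP 5.8:

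> Peak ketone concentration (Day 2) will be log-transformed and analysed with the same mixed model (treatment, period, sequence; subject within sequence random) in mFAS subjects with Day 2 ketone data in both periods and identical Day 2 initial correction-bolus doses, giving the geometric LS-mean ratio LY900014/Humalog and 95% CI, labelled exploratory, with no significance claim. A sensitivity run omits subjects given an additional or rescue bolus in either period.

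Keep the SAP 5.11 summaries. Add a table note that time from suspension to bolus varies, because a confirmed PG above 240 mg/dL triggers the bolus.

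The cost is two runs of an existing SAS model and two table rows, with no new data. The downside is one more exploratory estimate and its sensitivity run. Some pairs may be incomplete, because footnote 2 of protocol Table 3 ranks ketone samples behind PG and PK samples.

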5.12 Analysis of Plasma Glucose for Safety

Individual listings of blood glucose for safety will be presented by treatment.

Statistical Analysis Plan				
Trial ID	EudraCT-No.	Date	Status / Version-No.	Page
I8B-MC-ITST	2019-003493-13	15 Jul 2020	Final 1.0	37 of 47

5.13 Analysis of Other Assessments

Concomitant medication data will be presented by individual listings. In addition, tabular summaries will be done.

Pregnancy test data, alcohol test and body weight will be presented by individual listings. In addition, tabular summaries will be done.

Carbohydrates at standard liquid meal (in detail: Total estimated carbohydrates for a complete meal are 63 g, Total estimated carbohydrates for a complete meal, Meal consumed completely? Non-consumed carbohydrate amount, Consumed amount of carbohydrates, Consumed amount of carbohydrates [%]) will be presented by individual listings. The meals will be consistent for both treatment periods and for all individual subjects. However, adaptations in the planned amounts can be done for an individual subject when experience is gathered during the experimental procedures. In addition, tabular summaries will be done.

5.14 Subject Disposition

Disposition of subjects will be tabulated including:

- Number of Screened Subjects
- Number of Screening Failures
- Number of randomised subjects
- Number and percent of subjects exposed to LY900014 and Humalog[®]
- Number and percent of subjects exposed to LY900014 and Humalog[®] (infusion via pump/ Day 1)
- Number and percent of subjects exposed to LY900014 and Humalog[®] (injection via syringe/ Day 2)
- Number and percent of completers
- Number and percent of discontinued subjects
- Number and percent of subjects in each analysis set

The calculation of percent will be based on the number of randomised subjects. Subject disposition and observations excluded from analysis sets will be listed.

5.15 Treatment Compliance

Administered doses (basal rate and bolus) of IMPs will be listed and summarized by treatment and dosing day, including body weight and basal insulin suspension/ bolus administration.

Statistical Analysis Plan				
Trial ID	EudraCT-No.	Date	Status / Version-No.	Page
I8B-MC-ITST	2019-003493-13	15 Jul 2020	Final 1.0	38 of 47

5.16 Important Protocol Deviations

Important protocol deviations will be listed.

5.17 Screening Failures and Discontinuations

A listing of subjects who discontinued from the trial by reason for termination and a separate listing for all screening failures will be presented.

5.18 Interim Analysis

No interim analysis is planned. If an unplanned interim analysis is deemed necessary, the Lilly clinical pharmacologist, CRP/investigator, or designee will consult with the appropriate medical director or designee to determine if it is necessary to amend the protocol.

The Lilly study team is unblinded; the investigator shall remain blinded until database lock is achieved. Data may be analyzed by the Lilly study team while the trial is ongoing but no changes to the study design are planned. No assessment committee will be formed.

Statistical Analysis Plan				
Trial ID	EudraCT-No.	Date	Status / Version-No.	Page
I8B-MC-ITST	2019-003493-13	15 Jul 2020	Final 1.0	39 of 47

6 ITEMS FOR STATISTICAL DOCUMENTATION

The statistical documentation to be included in an appendix to the CSR will include:

- SAP
- Relevant output from statistical analyses

Statistical Analysis Plan				
Trial ID	EudraCT-No.	Date	Status / Version-No.	Page
I8B-MC-ITST	2019-003493-13	15 Jul 2020	Final 1.0	40 of 47

